6.2 Subject Compliance

For the subject with follow-up visits during the study, the "dose to be administered" refers to the total dose of a drug scheduled to be administered by the subject in a certain study phase (e.g., introduction period or treatment phase). For the subject who withdraws from the study early, the "dose to be administered" refers to the dose that should be taken from the beginning of a certain study phase to the day when the investigational drug is administered at the end of this study. Actual dose of the subject: dose dispensed - dose recovered - dose lost (the dose should be checked with the medication records in the subject diary, and the actual medication should be inquired and recorded in detail).

Compliance =
$$\frac{\text{Actual dose of the subject}}{\text{Dose to be administered of the subject}} \times 100\%$$

7. EFFICACY EVALUATION

7.1 Primary Efficacy Endpoint:

Changes in HbA1c from baseline with 12-week treatment.

7.2 Secondary Efficacy Endpoints

- 1. Percentage of subjects with HbA1c < 6.5% at Week 8 and 12.
- 2. Percentage of subjects with HbA1c < 7% at Week 8 and 12.
- 3. Changes in fasting blood glucose from baseline at Week 4, 8, and 12.
- 4. Changes in postprandial blood glucose from baseline at Week 8 and 12.
- 5. Changes in fasting insulin level from baseline at Week 4, 8, and 12.
- 6. Changes in postprandial insulin level from baseline at Week 8 and 12.
- 7. Changes in fasting C-peptide from baseline at Week 4, 8, and 12.
- 8. Changes in postprandial C-peptide from baseline at Week 8 and 12.
- 9. Changes in serum ALT, AST, GGT, and TBIL from baseline at Week 4, 8, and 12.
- 10. Changes in CAP measured by liver transient elastography from baseline with 12-week treatment.

Protocol No.: HTD1801.PCT103

- 11. Changes in C-reactive protein from baseline with 12-week treatment.
- 12. Changes in serum LDL-C, high-density lipoprotein cholesterol (HDL-C), triglycerides (TG), total cholesterol (TC) from baseline at Week 4, 8, and 12.
- 13. Changes in body weights of subjects from baseline at Week 4, 8, and 12.
- 14. Changes in medication for blood lipid control in subjects from baseline with 12-week treatment.
- 15. Evaluation on the PPK parameters of multiple-dose of HTD1801 in T2DM patients.
- 16. Changes in characteristics of intestinal flora from baseline at Week 8 and 12.
- 17. Changes in characteristics of intestinal flora metabolites from baseline at Week 8 and 12.

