- 13. Subjects who have used insulin or its analogs for more than 2 consecutive weeks within 12 months prior to screening (use of insulin or its analogs for hyperglycemia during pregnancy prior to screening is not within the scope of this limitation);
- 14. Subjects who have used ≥2 types of hypoglycemic drugs with different mechanisms prior to screening for more than 8 weeks and within 12 months (use of insulin or its analogs for hyperglycemia during pregnancy prior to screening is not within the scope of this limitation).
- 15. Subjects who have used any drugs that may affect blood glucose metabolism within 8 weeks prior to screening, such as hypoglycemic drugs (including traditional Chinese medicines indicated for hypoglycemic therapy), systemic glucocorticoids (except for inhalation, eye instillation, and topical skin drugs), growth hormone, non-selective β-receptor blockers (such as propranolol, etc.), thiazide diuretics at a dose of >25 mg/day or aspirin at a dose of >300 mg/day, etc.
- 16. Subjects who have used liver-protecting drugs (including traditional Chinese medicine) or dietary supplements within 4 weeks prior to screening (see APPENDIX 1).
- 17. Subjects who have used any chemical drugs, traditional Chinese medicines or dietary supplements for weight loss (see APPENDIX 2), participated in a weight loss program, or followed a special diet within 4 weeks prior to screening.
- 18. Subjects who have used antibiotics (except for topical application) within 4 weeks prior to screening.
- 19. Subjects who have been administered with probiotic-containing drugs or dietary supplements within 4 weeks prior to screening or prior to randomization (V3) (see APPENDIX 3).
- 20. Subjects who have used lipid-lowering drugs at stable doses <4 weeks prior at screening (V1).
- 21. Subjects who have uncontrolled hypertension (systolic blood pressure >160 mmHg and/or diastolic blood pressure >100 mmHg) at screening (V1) or before randomization (V3).

22. Subjects who have abnormal thyroid function that cannot be controlled with drugs at stable doses, or clinically significant abnormality in thyroid function test results that requires drug treatment at screening (V1).

Protocol No.: HTD1801.PCT103

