6. CONCOMITANT/PROHIBITED MEDICATIONS AND TREATMENT

6.1 Concomitant Medication

6.1.1 Allowed concomitant medications/treatment:

Without the consent of the investigator, no other hypoglycemic drugs other than the investigational drug can be used throughout the study, except for the drugs used for the treatment of AEs. Concomitant drugs (such as antihypertensive, lipid-lowering drugs) before the study should continue to be used at their original doses, and the reasons for their use should be fully recorded in the eCRF. Any new concomitant medications/treatments, or changes in concomitant medication doses, and the reason for medication, dates of administration (including start and end dates), and dosing information (including dose, route, frequency) must be recorded in the corresponding section in the eCRF from the signing of the ICFs through the entire treatment phase and during the safety follow-up visit.

Protocol No.: HTD1801.PCT103

6.1.2 Prohibited concomitant medications/treatment:

The following limitations on prohibited concomitant treatments or drugs do not apply to the salvage therapy administered to subjects by the investigator according to the protocol (see Section 5.1.3.3). During the period from the subject signs the ICFs to the end of the double-blind phase (excluding the safety follow-up visit phase and early withdrawal visit), the prohibited concomitant treatments include:

- Any drugs that may affect blood glucose metabolism, such as:
- Hypoglycemic drugs (including traditional Chinese medicines indicated for hypoglycemic therapy)
- Systemic glucocorticoids (except inhalation, eye instillation, and topical dermal application)
- Growth hormone
- Non-selective β-receptor blockers (such as propranolol, etc.)
- Thiazide diuretics at a dose > 25 mg/day
- Aspirin at a dose >300 mg/day
- Thyroid hormones: During the study, no new thyroid hormone drugs or changes in the previous drug regimen (except stable replacement therapy) are allowed.
- Liver-protecting drugs (including traditional Chinese medicine) or dietary supplements (see APPENDIX 1)
- Any chemical drugs, traditional Chinese medicines or dietary supplements for weight loss (see APPENDIX 2), a weight loss program, or a special diet.
- robiotic-containing drugs or dietary supplements (see APPENDIX 3).
- New use of drugs for controlling blood lipid and blood pressure, or changes in previous drug regimens
- Blood transfusion or use of blood products is required.

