- Vaccines (except for inactivated vaccines).
- Drugs or treatments that, in the judgment of investigators, may affect the objectivity of the assessment of safety and/or efficacy of subjects in this study.

• Traditional Chinese Medicine.

Unless in emergencies, subjects are prohibited from using any new drug that is not reported during the screening phase without prior consultation with the investigator or self-adjusting the dose of concomitant drugs during the study. In emergencies, if there is a clinical indication for the use of a new drug or dose modification of the concomitant drug, the subject must notify the investigator before using the concomitant drug. The investigator will determine and record any emergency medication's usage, name, dose, route of administration, objectives of treatment, and date of administration.

Protocol No.: HTD1801.PCT103

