10.4.4 Secondary efficacy analysis

Secondary endpoints are as follows:

- 1. Percentage of subjects with HbA1c < 6.5% at Week 8 and 12.
- 2. Percentage of subjects with HbA1c < 7% at Week 8 and 12.
- 3. Changes in fasting blood glucose from baseline at Week 4, 8, and 12.
- 4. Changes in postprandial blood glucose from baseline at Week 8 and 12.
- 5. Changes in fasting insulin level from baseline at Week 4, 8, and 12.
- 6. Changes in postprandial insulin level from baseline at Week 8 and 12.
- 7. Changes in fasting C-peptide from baseline at Week 4, 8, and 12.
- 8. Changes in postprandial C-peptide from baseline at Week 8 and 12.
- 9. Changes in serum ALT, AST, GGT, and TBIL from baseline at Week 4, 8, and 12.
- 10. Changes in CAP measured by liver transient elastography from baseline with 12-week treatment.
- 11. Changes in C-reactive protein from baseline with 12-week treatment.
- 12. Changes in serum LDL-C, HDL-C, TG, and TC from baseline at Week 4, 8, and 12.

- 13. Changes in body weights of subjects from baseline at Week 4, 8, and 12.
- 14. Changes in medication for blood lipid control in subjects from baseline with 12-week treatment.

Protocol No.: HTD1801.PCT103

For the measurement data in the secondary efficacy endpoints, the same analysis method as the primary efficacy endpoints is used, with the random stratification factors in the model: CAP and HbA1c; for the enumeration data in the secondary efficacy endpoints, invalid filling is applied and the CMH method is used for inter-group comparison, with the random stratification factors in the model: CAP and HbA1c.

Study Objectives	Endpoints	Estimated Objective	

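### Secondary efficacy endpoint 14 (change in lipid-control medication) is near-constant by design, because section 6.1 holds lipid drugs fixed over the same 12 weeks

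*Protocol*

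**What the plan says.** Protocol 7.2, item 14, is "Changes in medication for blood lipid control in subjects from baseline with 12-week treatment". The same line stands among the secondary efficacy endpoints in the synopsis and as item 14 in 10.4.4. No category, direction or definition of success is attached to it in any of the three places.

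Section 6.1.1 states: "Concomitant drugs (such as antihypertensive, lipid-lowering drugs) before the study should continue to be used at their original doses". Section 6.1.2 lists among prohibited treatments "New use of drugs for controlling blood lipid and blood pressure, or changes in previous drug regimens", and the list applies "During the period from the subject signs the ICFs to the end of the double-blind phase". The only exemption stated for the list is the protocol's own salvage therapy, which is a glucose-lowering drug. Exclusion criterion 20 (3.2) also keeps out subjects whose lipid-lowering dose has been stable for less than 4 weeks at screening.

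Two provisions soften this. Section 6.1.1 requires that "Any new concomitant medications/treatments, or changes in concomitant medication doses, and the reason for medication" be recorded in the eCRF, with dates and dosing. The end of 6.1.2 makes room for exceptions, on advance notice to the investigator: "In emergencies, if there is a clinical indication for the use of a new drug or dose modification of the concomitant drug".

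Section 10.4.4 gives two analysis routes. Measurement data follow the primary method (MMRM, with LOCF ANCOVA as sensitivity analysis). For counts and categories, "for the enumeration data in the secondary efficacy endpoints, invalid filling is applied and the CMH method is used for inter-group comparison", with CAP and HbA1c as stratification factors. The protocol does not say which route endpoint 14 takes.

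**The concern.** An efficacy endpoint has to be free to respond to treatment. If HTD1801 lowered lipids enough that fewer subjects needed a statin, or smaller doses, this endpoint is where it should show. Section 6.1 prevents that response during the whole window in which it is measured, in every arm.

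The endpoint nevertheless stays in the list that 10.4.4 sends to formal between-group analysis. A null result could then be read as no effect on the need for lipid drugs, and a nominal difference as an effect. Neither reading would be sound, since the changes that remain possible come from emergencies and non-adherence, and missing outcomes may add to them.

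**Working it through.** **1. Is there a figure in the plan to reproduce?** None exists for endpoint 14. The planning figures used below come from 10.2: 33 enrolled per group, 27 evaluable, dropout of approximately 20%. The implied dropout is 1 − 27/33 = 18.2%, consistent with that description. The primary-endpoint power also reproduces: a two-sample t-test with 27 per group and SD 1.1 gives 90.6% for a difference of 1.0 and 63.1% for 0.7, against the stated 90% and 63%. None of this is in dispute.

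**2. Do the windows overlap?** The endpoint runs from baseline to Week 12. The prohibition runs from consent to the end of the 12-week double-blind phase. The endpoint window lies wholly inside the prohibition window.

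**3. What can each analysis route deliver?** Let *d* be dropout and *q* the share of completers whose lipid medication changes despite the rule, through an emergency or a deviation. Both *q* and any arm-specific *d* are assumptions; the protocol gives neither.

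*Measurement route.* Adherent subjects all score zero, and LOCF carries a zero forward. The model has almost no variance to explain.

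*Categorical route, success = lipid drug reduced or stopped.* This assumes that 'invalid filling' means missing = failure, and that every change is a reduction. Expected successes per arm = 33 × (1 − 0.20) × *q* = 26.4*q*.

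| *q* | Expected successes per arm |
|---|---|
| 0 | 0 |
| 2% | 0.5 |
| 5% | 1.3 |

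At *q* = 0 no arm has a success, whatever the dropout, and the test is degenerate.

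*Categorical route, success = no adverse change.* This assumes missing = failure, that every change is adverse, and that each dropout lacks a Week 12 status. The success rate is (1 − *d*)(1 − *q*), and the share of failures that are dropouts is *d* / [1 − (1 − *d*)(1 − *q*)]. With *d* = 0.20:

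| *q* | Calculation | Share |
|---|---|---|
| 0 | 0.20 / 0.200 | 100% |
| 2% | 0.20 / 0.216 | 93% |
| 5% | 0.20 / 0.240 | 83% |
| 10% | 0.20 / 0.280 | 71% |

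**4. Could this produce a false signal?** Only if dropout differs between arms. With *q* = 0 the success rate is 1 − *d*. The chance that an unstratified two-sided 5% comparison at 33 per arm rejects in the direction of the dropout difference is Φ[(Δ − 1.96·SE0)/SE1], with SE0 pooled and SE1 unpooled.

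- Dropout 10% vs 30%: Δ = 0.20, SE0 = √(2 × 0.8 × 0.2/33) = 0.0985, SE1 = √((0.09 + 0.21)/33) = 0.0953. The result is about 53%.
- Dropout 15% vs 25%: Δ = 0.10, SE0 = 0.0985, SE1 = √((0.1275 + 0.1875)/33) = 0.0977. The result is about 17%.
- Equal dropout: no expected difference between arms.

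These pairs are illustrations of sensitivity and do not forecast this trial.

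**The case against.** The best defence is that the endpoint is not strictly constant. The protocol foresees drug changes in emergencies and has all changes recorded with reasons. A reader might infer from 6.1.2 that endpoint 14 cannot vary at all, or that every change is a protocol deviation. The documents do not support either: an emergency change is provided for, and calling it a deviation would misclassify it. This part of the defence stands. It does not rescue the endpoint, because emergencies and non-adherence do not measure a drug effect on the need for lipid treatment.

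A second stronger inference is that the planned test simply compares dropout, with 99 × 0.20, or about 20, imputed failures against no real events. That would need four things the protocol does not settle: that endpoint 14 is categorical, that 'invalid filling' means missing = failure, that success means no adverse change, and that withdrawers have no usable value. Under another definition of success the test is degenerate instead. Equal dropout creates no expected difference. Early leavers are also recommended to attend a withdrawal visit with the V7 procedures, where concomitant medication is recorded, so leaving early need not mean missing data.

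It can also be said that coding and missing-data rules belong in the statistical analysis plan. That is fair for those rules, and their absence is not the point here. No coding rule can create variation that section 6.1 removes.

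Finally, the study is exploratory with no alpha correction, this is one of 17 secondary items in 7.2, and item 12 measures lipids directly. All true; this limits the weight of the point.

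**Conclusion.** The point holds in this form: 7.2 and 10.4.4 make change in lipid-control medication an efficacy endpoint, while 6.1.1 and 6.1.2 hold that medication fixed over the same period. Outside emergencies and deviations the endpoint takes one value in all arms. It therefore cannot support an efficacy conclusion under either route in 10.4.4.

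That conclusion rests only on the protocol text. The sizes are conditional. The 71% to 93% dropout share assumes 20% dropout, missing = failure, no Week 12 status for dropouts, success meaning no adverse change, and 2% to 10% of completers changing. The 0.5 to 1.3 expected successes assume that success means a reduction and that 2% to 5% of completers reduce. The rejection rates of about 53% and 17% further assume unequal dropout. It would go too far to state as fact that the result will be a comparison of dropout.

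The consequence is confined to one exploratory secondary endpoint. The primary HbA1c analysis and the sample size are untouched.

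**What to change.** Reconcile section 6.1 with endpoint 14. Which of the two gives way is a clinical decision for the sponsor. While the prohibition stands:

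1. Remove endpoint 14 from the formally tested efficacy endpoints in the synopsis, 7.2 and 10.4.4.
2. Report lipid-drug changes descriptively by arm, with reasons, separating emergency changes from deviations.
3. Name a lipid-drug change as an intercurrent event and add a sensitivity analysis of LDL-C, HDL-C, TG and TC that accounts for it. The estimand table in 10.4.4 names only salvage therapy as such an event.

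If the sponsor instead revises section 6.1 so that the endpoint can respond, the protocol should then define its categories, its direction and what counts as success.

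The cost under the standing prohibition is one line removed in three places, one table or listing, and one sensitivity analysis. No new data are needed, because 6.1.1 already requires changes, reasons, dates and doses to be recorded.

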7.3 Safety Indicators

The following indicators need to be recorded for the safety evaluation of the drug:

- AEs
- Hypoglycemia events (see Section 3.3.1.1 for definition of hypoglycemia)
- Clinical laboratory tests
- 12-lead ECG
- Vital signs
- Physical examination

7.3.1 Physical examination

Physical examinations: including skin, mucous membranes, lymph nodes, head, neck, chest, Study Protocol: Version 2.0/Date: 4/27/2022 Confidential Page 58

abdomen, spine/limbs.

7.3.2 Vital signs

Pulse, temperature, sitting blood pressure (systolic and diastolic) measurement. Subjects should be measured at rest. It is recommended that blood pressure be measured on the same arm for each subject at each visit throughout the study.

Protocol No.: HTD1801.PCT103

7.3.3 12-lead ECG

The subject should receive the 12-lead ECG in the supine position after rest. The heart rate, PR interval, QT interval, RR interval, QTcF (see APPENDIX 5 for calculation formula) and QRS complex duration should be recorded. In the event of an abnormal ECG during the visit, the investigator and/or authorized investigator may decide whether to repeat the test based on the subject's clinical condition and evaluate the test results. An unscheduled visit for a 12-lead ECG may also be arranged if clinically indicated.

7.3.4 Clinical laboratory tests

The investigator must evaluate all values outside the normal range (CS: abnormalities with clinical significance, NCS: abnormalities without clinical significance), with signature and date. An AE is recorded only when the CS value judged by the investigator meets the definition of AEs. In the study, the investigator may decide to conduct additional or repeated tests if necessary.

For items (such as hematology) listed in the laboratory test report according to Good Laboratory Practice, but not required in the study protocol, it is no need to record them in the eCRF.

7.3.5 Pregnancy test

Female subjects of childbearing age should receive the blood pregnancy test in local laboratories at V1, V3, and V7 (or withdrawal visit) (see APPENDIX 6). During the study V5 and V6, female subjects of childbearing age should receive the urine pregnancy test in local laboratories, and if the urine pregnancy test is positive, a blood pregnancy test should be performed immediately to exclude or verify the pregnancy. If the V1 blood pregnancy test is positive, the subject will not be able to participate in the study. Female subjects should withdraw from the study immediately once the blood pregnancy test is positive during the study.

7.3.6 Self-Monitoring of Blood Glucose (SMBG)

In the introduction period, investigators should instruct subjects on the precautions for SMBG operation and remind them to record the test results in the subject diary in time as required. During the study, if any problem with the subject's operation or recording is found, repeated or targeted training should be given in time to improve the compliance of the operation.

During this study, subjects should undergo SMBG test under the guidance of the investigator. In case of poor blood glucose control, blood glucose monitoring at corresponding time points can be increased according to the guidance of the investigator. If there are suspected symptoms of hypoglycemia, the blood glucose should be measured as soon as possible; if nocturnal hypoglycemia is suspected, the nighttime self-monitoring of blood glucose should be increased according to the guidance of the investigator. The above blood glucose results should be recorded in the subject diary in time. SMBG procedures are detailed in APPENDIX 10.

7.4 Pharmacokinetic Endpoints

HTD1801 plasma concentration.

The blood volume, processing, transportation and preservation of samples are described in the

central laboratory SOP (see Laboratory Operation Manual).

Protocol No.: HTD1801.PCT103

8. ADVERSE EVENTS

8.1 Definitions

8.1.1 Adverse events

An Adverse Event (AE) is defined as any untoward medical event that occurs after a subject receives the investigational drug, which may be manifested as symptoms, signs, diseases, or laboratory abnormalities, but may not necessarily have a causal relationship with the investigational drug. Therefore, an AE can be any unfavorable or undesirable symptoms, signs, or diseases, including adverse drug reactions, critical laboratory abnormalities, and diseases during the study.

Protocol No.: HTD1801.PCT103

AEs do not include:

- ➤ Diseases, conditions, or laboratory abnormalities that have existed or been detected prior to screening or baseline but not worsen;
- There are no adverse medical events (e.g., hospitalization for elective surgery, social reasons, and/or self-convenience);
- Any medical condition or clinically significant laboratory test abnormality that occurs before the signing of the ICFs and is not related to the study procedures is not considered an AE, and is considered pre-existing.

8.1.2 Hypoglycemia event

The date and time of onset and end of each hypoglycemia event, the classification of hypoglycemia (for the definition of hypoglycemia, see Section 3.3.1.1), blood glucose value and/or description of symptoms, measures taken and description, the determination that whether it is severe hypoglycemia and whether it is resolved, cause and description, the correlation judgment with the investigational drug and the correlation judgment with the salvage therapy drug, etc. should be recorded in detail.

